9.11.4. Electrocardiogram (ECG)

The following ECG measurements will be summarized:

- Heart rate
- RR interval (msec)
- QRS interval (msec)
- QT interval (msec)
- Fridericia corrected QT (QTcF) interval [$QTcF = QT/\sqrt[3]{RR/1000}$]

An overall investigator assessment of ECG will be provided (categories "normal", "abnormal, not clinically significant" and "abnormal, clinically significant"). The following categories will also be reported for QTcF:

- QTcF > 450 msec
- QTcF > 480 msec
- QTcF > 500 msec
- Change from baseline in QTcF > 30 msec
- Change from baseline in QTcF > 60 msec

The ECG measurements and changes from baseline in ECG will be summarized by treatment, visit with descriptive statistics for the SAF.

All ECG data will also be presented in listings.

9.11.5. Vital Signs

The following vital signs will be summarized:

- Systolic and diastolic blood pressure (mmHg)
- Heart rate (beats/minute)
- Respiration rate (breaths/minute)
- Body temperature (°C)
- Weight (kg)

Observed values and changes from baseline in vital signs will be summarized by treatment and visit using descriptive statistics for the SAF. By-participant listings will also be presented.

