5.2. Risk-benefit Assessment

Patients diagnosed with malignant solid tumors or TGCT have enrolled in Phase 1/2 Study DCC-3014-01-001. As of 09 Nov 2021, approximately 54% of patients experienced adverse events (AEs) of Grade 3 or higher. Treatment-emergent AEs of Grade 3 or higher reported in more than 1 TGCT patient were blood creatine phosphokinase (CPK) increased 29 (33.3%), aspartate aminotransferase (AST) increased 4 (4.6%), hypertension 4 (4.6%), lipase increased 3 (3.4%), and amylase increased 3 (3.4%). Observed elevations in transaminase were not associated with symptoms and were not accompanied by bilirubin elevations and/or other signs of liver damage. Safety laboratory values, cardiac function, and clinical signs and symptoms will be monitored throughout the study. Dosing modification guidelines are included in the protocol for AE monitoring (see Section 9.6). Please refer to the Investigator's Brochure (IB) for currently available clinical safety data.

Effects on embryo-fetal development were studied in rats, and vimseltinib was determined **CC** Participants in this study are advised to avoid pregnancy and are required to use highly effective contraception during the study and for 60 days following the last dose of study treatment for females and 120 days for males. Additional details on the available nonclinical toxicology data and clinical safety data are provided in the IB.

Among efficacy evaluable TGCT patients, objective responses were observed as measured by Response Evaluation Criteria in Solid Tumors (RECIST) v1.1 by independent radiological review (IRR) that were sustainable over time. Updated anti-tumor activity data as of 07 Jun 2021 demonstrated an objective response rate (ORR) of 50% in 32 patients across 3 dose escalation cohorts, and an ORR of 42% (all partial response [PR]) in 19 patients in expansion Cohort A at the recommended Phase 2 dose (RP2D), which is also the selected Phase 3 dose. Objective responses were generally achieved after at least 2 cycles of treatment and responses were durable.

The clinical experience continues to support further study of vimseltinib in the TGCT patient population. The risk to participants appears acceptable, and the benefit-risk balance of vimseltinib treatment in TGCT patients for the Phase 3 study is considered positive.

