12.4.6. Safety Analyses

Participants from the Safety Set will be included in safety analyses.

AEs will be coded using the MedDRA for purposes of summarization. All AEs occurring on study will be listed in by participant data listings. Treatment-emergent AEs will be tabulated, where treatment emergent is defined as any AE that occurs after administration of the first dose of study drug and through 30 days after the last dose of study drug. Tabulations for all TEAEs, treatment-emergent SAEs, related TEAEs, dose reduction, dose interruptions, and discontinuation of study drug due to AE will be produced. By participant listings will be provided for deaths, SAEs, and AEs leading to discontinuation of study drug.

Change from baseline in clinical laboratory parameters will be summarized across time on study, and the frequency of clinically significant abnormal laboratory values will be tabulated.

Changes in ECG intervals (QT, RR, QTcF, HR, QRS) and vital sign parameters (including systolic and diastolic blood pressure, heart rate, respiration rate, and temperature) will be summarized over time in a similar fashion to laboratory parameters, and any abnormal values will be tabulated. Changes in ECG findings will be presented in data listing format.

Additional safety assessments such as ECGs will be listed by participant.

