9.1. General Methods

Data collected in this study will be documented using summary tables and participant data listings. Continuous variables will be summarized using descriptive statistics (number of observations, mean, median, standard deviation, minimum, and maximum). Categorical variables will be summarized using frequencies and proportions. Time-to-event data will be summarized via Kaplan-Meier (KM) methodology using the 25th, 50th (median), and 75th percentiles with associated 2-sided 95% confidence intervals (CIs).

Medical history, AEs, and concurrent procedures will be coded using Medical Dictionary for Regulatory Activities (MedDRA) version 26.0 (or higher). Prior and concomitant medications will be coded using the World Health Organization (WHO) Drug Dictionary March 2023 Global B3 or later.

This study comprises 2 periods: the randomized double-blinded period (Part 1) and the open-label portion that occurs after unblinding the study treatment at Week 25 (or earlier if there is a treatment discontinuation due to a centrally confirmed disease progression) (Part 2).

Unless otherwise specified, the ITT and PP Sets are used for efficacy analysis and the SAF is used for the safety analysis.

The primary analysis will be conducted at the earliest when all participants have completed the double blinded treatment period (Part 1).

In general, unless otherwise specified, data summaries will be presented by treatment group (vimseltinib versus placebo) and overall. Between-group comparisons will focus on the comparative performance of vimseltinib versus placebo. All statistical tests will be conducted at a 2-sided significance level of 0.05.

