11. CHANGES TO PLANNED ANALYSIS IN PROTOCOL

[figure not shown]
There are no major changes from the protocol planned analyses.

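### SAP 9.11.5 omits the table of abnormal vital signs promised in Protocol 12.4.6, and SAP Section 11 does not record the change, so no by-arm count of participants with abnormal measured blood pressure is planned

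*SAP*

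**What the plan says.** Protocol 12.4.6 (Safety Analyses) treats ECG intervals and vital signs in one sentence. It names systolic and diastolic blood pressure, heart rate, respiration rate and temperature, and states that changes in them "will be summarized over time in a similar fashion to laboratory parameters, and any abnormal values will be tabulated".

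SAP 9.11.5 (Vital Signs) lists the same parameters plus weight. It then plans: "Observed values and changes from baseline in vital signs will be summarized by treatment and visit using descriptive statistics for the SAF". It closes with: "By-participant listings will also be presented". It contains no abnormal-value table, threshold, grade or shift table.

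SAP 9.1 defines descriptive statistics for continuous variables as the number of observations, mean, median, standard deviation, minimum and maximum.

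SAP Section 1 makes the SAP the primary reference where it differs from the protocol, and says that any differences will be highlighted in Section 11. Section 11 reads: "There are no major changes from the protocol planned analyses". It does not mention vital signs.

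Protocol 5.2 reports hypertension in 4 (4.6%) TGCT patients. It is one of five treatment-emergent events of Grade 3 or higher that occurred in more than one TGCT patient in the Phase 1/2 study.

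**The concern.** The protocol commits to a safety output that the governing analysis document does not contain, and the section reserved for such differences is silent. The ECG half of the same protocol sentence was carried over at least in part: SAP 9.11.4 adds an overall normal/abnormal assessment and states "The following categories will also be reported for QTcF", followed by five threshold categories. The vital-signs half has no counterpart.

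What is at stake is the by-arm summary of measured blood pressure, for a drug with a prior Grade 3 or higher hypertension signal. If a few percent of participants have marked rises, the useful summary is how many in each arm, out of how many. Without it, the only planned counts of hypertension come from adverse-event reports, which depend on the investigator judging the reading clinically significant. A table of measured values is the usual check on that reporting.

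**Working it through.** **Step 1: the Phase 1/2 figure.** Protocol 5.2 does not print the number of TGCT patients, so it has to be inferred. It gives 29 (33.3%) for raised CPK and 4 (4.6%) for hypertension. Among whole numbers from 50 to 139, only N = 87 reproduces both: 29/87 = 33.3% and 4/87 = 4.60%. The exact 95% confidence interval for 4/87 is 1.3% to 11.4%.

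**Step 2: expected cases here.** With about 80 participants on vimseltinib (Protocol 12.1), 80 × 4/87 = 3.7. Over the interval the range is 80 × 0.0127 = 1.0 to 80 × 0.1136 = 9.1. This assumes that the Phase 1/2 rate carries over. Protocol 5.2 ties the four cases neither to the Phase 3 dose nor to an exposure time.

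**Step 3: would visit means show it?** The documents give neither the size of the rise nor the standard deviation, so both are assumptions shown as ranges. Suppose that 4.6% of the vimseltinib arm is raised by d at the same visit and that everyone else, including the placebo arm, is unchanged.

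- Shift in arm mean = 0.046 × d: 0.9 mmHg at d = 20, 1.4 at 30, 1.8 at 40 and 2.3 at 50.
- Standard error of the difference = SD × √(1/80 + 1/40) = SD × 0.1936: 1.9 mmHg at SD 10 and 2.9 mmHg at SD 15.
- Ratio: from 0.9/2.9 = 0.3 to 2.3/1.9 = 1.2 standard errors.

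A by-visit mean would therefore hardly show the effect.

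**Step 4: do the other planned outputs give the count?**

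| Output | What it shows | What it does not give |
|---|---|---|
| By-visit maximum (SAP 9.1, 9.11.5) | The single highest value per arm and visit | How many participants were high |
| Listings (SAP 9.11.5) | Every reading | Any count or percent by arm |
| TEAE tables (SAP 9.11.2) | Hypertension reported as an event, by preferred term and maximum grade | Abnormal readings not judged clinically significant |

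Two limits apply to the maximum. First, with 2:1 allocation it tends to be higher in the larger arm even without a drug effect. For normal data the expected maximum is 2.43 SD in 80 and 2.16 SD in 40, a gap of 0.27 SD, or about 3 to 4 mmHg for SD 10 to 15. Second, under SAP 8.3 and 8.4.1, unscheduled readings that cannot be mapped to a visit are left out of by-visit summaries.

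On the adverse-event route, Protocol 11.9.14.3.8.1 calls an abnormal assessment clinically significant if it comes with worsening related signs or symptoms, needs further testing or intervention, or leads to a study-drug change. A raised reading that meets none of these need not become an adverse event.

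**The case against.** The strongest reply is that hypertension remains well covered. Clinically significant vital signs must be recorded as adverse events. SAP 9.11.2 tabulates those by preferred term and maximum grade, and Grade 3/4 events by preferred term, for each treatment group. The 4 (4.6%) in Protocol 5.2 is itself an adverse-event count, so the SAP keeps the type of output that revealed the signal and adds a placebo comparison. The listed secondary endpoint is change from baseline in vital signs, which SAP 9.11.5 delivers. Section 11 denies only major changes, and one missing descriptive table may be thought minor. The protocol sentence asks for no CTCAE grades and no shift from baseline.

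Most of this stands, and it rules out two stronger readings. A reader might infer that vital signs are cut down to means and listings, so that hypertension could not be seen in the measured pressures. The documents do not support that: the descriptive statistics include the median, standard deviation, minimum and maximum, and every reading is listed. A reader might also infer that vital signs alone were stripped of abnormal-value outputs. That is wrong too. The CTCAE shift table in SAP 9.11.3 covers only hematology and serum chemistry, so coagulation and urinalysis have none. In SAP 9.11.4 only QTcF has threshold categories, and the other ECG measurements have none.

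The reply does not supply the promised count of abnormal measured values. Nor does the word major settle the Section 11 question, because SAP Section 1 says that any differences will be highlighted there.

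**Conclusion.** The point holds as an undisclosed gap between protocol and SAP. The protocol promises a tabulation of abnormal vital signs, the SAP does not plan it, and Section 11 does not say so. The consequence is limited: no by-arm number and percent of participants with abnormal measured blood pressure, for an event expected in about 3.7 of 80 vimseltinib participants (1.0 to 9.1) if the Phase 1/2 rate applies. It does not follow that a blood-pressure effect would go unseen, and no efficacy or multiplicity conclusion is touched.

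The discrepancy itself rests on the text alone. The expected count rests on the inferred denominator of 87 and on the rate carrying over. The comparison of mean shift with standard error rests on assumed rises and standard deviations and is only an illustration. The change should be made because it restores a stated commitment at little cost.

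**What to change.** Before unblinding, add to SAP 9.11.5 the number and percent of participants, by arm, with abnormal post-baseline vital signs, including worst post-baseline systolic and diastolic pressure set against baseline. Produce it for both safety approaches in SAP 9.11: the Part 1 comparison and the combined on-vimseltinib summary. State that unscheduled readings count towards the worst value.

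Prespecify the analysis categories, since neither document defines abnormal limits for any vital sign. The CTCAE v5.0 grading already used in the SAP is one option for blood pressure. The worst-value-against-baseline layout goes beyond the protocol's wording. The minimum is the promised abnormal-value table or, failing that, an entry in Section 11 that records and justifies its omission.

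The cost is two or three extra tables from data already collected, with no new assessments.

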10. INTERIM ANALYSIS

No interim analysis will be performed for this study.

11. CHANGES TO PLANNED ANALYSIS IN PROTOCOL

[figure not shown]
There are no major changes from the protocol planned analyses.

APPENDIX 1.

Figure 1: Study Schema

Patient population:

- Histologically confirmed, symptomatic tenosynovial giant cell tumors
- Surgical resection will potentially cause worsening functional limitations or severe morbidity

No prior use of systemic therapy targeting CSF1 or CSF1R (except imatinib and nilotinib)

Abbreviations: biw=twice weekly; CSF1=colony-stimulating factor 1; CSF1R=colony-stimulating factor 1 receptor; MRI=magnetic resonance imaging; PRO=patient-reported outcome; ROM=range of motion.

^a Disease follow-up will be performed for up to 2 years.

Note: Participants will be eligible to receive study drug until radiological confirmation of disease progression (refer to protocol Section 10.5), unacceptable toxicity, withdrawal by participant, physician's decision, or commercial availability of vimseltinib and for as long as vimseltinib is being developed to support the indication, and continuation of treatment does not conflict with the Sponsor's right to terminate the study.

Signature Page for DCC-3014-03-001 SAP Final 2.0 09AUG2023

Approval	PPD
	Deciphera Pharmaceuticals, LLC 18-Aug-2023 16:22:49 GMT+0000
Approval	PPD
	Deciphera Pharmaceuticals, LLC 18-Aug-2023 16:23:36 GMT+0000
Approval	PPD
	Deciphera Pharmaceuticals, LLC 18-Aug-2023 16:47:15 GMT+0000

Veeva Vault RIM Document ID Number DCC-CLIN-001500
